The study consisted of the clinical observations and analysis of the author/independent examiner after assessing the performance data of individuals who used Obi for self-feeding. From the Abstract: "This descriptive study examined the functional performance of self-feeding in 19 individuals with upper extremity limitations using Obi, a robotic self-feeding device. Participants ranged in age from 8 to 60 years and were observed across various environments, including homes, simulated-home setups, clinics, and schools. Participants' performance with Obi was evaluated using observational methods and secondary data analysis. Results indicated that all participants successfully used Obi to feed themselves independently by activating switches connected to the device, with a 100% success rate in delivering food to their mouths by the final trial session. Different types of switches, customized according to the participants' needs, allowed for personalized feeding experiences and increased their social interactions with family and friends.

With Obi3's scope changes, this study will ensure the device can continue to be operated in accordance with its intended use, continue to meet user needs, and confirm a favorable benefit/risk ratio.

- b) An evaluation of clinical data that are relevant to the proposed clinical investigation.

A clinical evaluation has been conducted and documented within IFD-DES-021, Clinical Evaluation Plan (CEP) & Report (CER) pertaining to the Gen2 device in 2024. This document includes the results of a systematic literature review pertaining to powered feeding devices. The conclusion reads as follows:

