"Based on the successful review of all data included in this CER, it can be concluded that Obi is well documented in relation to safety and performance and suitable for use per its intended use. Consequently, there has not been identified any outstanding risks that will justify the enrollment of patients in a clinical study and as such, a clinical study is not necessary to demonstrate conformity with the requirements. A small number of non-safety related complaints and no product recalls related to the subject device were identified, and with an accumulated performance-related complaint ratio of 2% worldwide, this CER concludes that using Obi, which is a class I low risk medical device, is safe, compliant with state of the art, and that the risk level is acceptable when weighed against the benefits to the patient or even in comparison with the use of the similar devices. The overall benefit vs. risk ratio for Obi remains favorable. Based on

assessment of all available data in respect of Obi, it is considered that the subject device fully complies with the relevant GSPR in Annex I of the EU 2017/745 MDR.”

c) a description of the clinical development stage (see Annex I), if appropriate.

This study should be considered predominantly a post-market, non-interventional, observational study (Design Validation).

Obi Gen 3 is a production equivalent Class I medical device intended to assist individuals with upper extremity motor impairments in self-feeding. This usability study is situated in the design validation stage of the product lifecycle, consistent with requirements outlined in ISO 13485 and FDA Quality System Regulation (QSR 21 CFR Part 820.30(f)) for medical device design controls.

This investigation aims to validate that the design of Obi-Gen 3 meets the intended use and user needs as formally documented before broader commercialization. This study is not intended to evaluate safety or efficacy from a regulatory or therapeutic standpoint, as the device does not deliver treatment but facilitates an activity of daily living. Instead, it focuses on:

- Confirming that usability goals (e.g., efficiency, ease of use, satisfaction) are met,
- Gathering qualitative feedback from key user stakeholders (providers, caregivers, patients) and
- Informing whether the design is ready for commercialization and on design enhancements, user support documentation, and deployment strategies.

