feeding for individuals with upper extremity impairments—a key activity of daily living that contributes to personal dignity, autonomy, and quality of life.

The claims for clinical performance and effectiveness to be verified in this study include:

- The device can be safely and effectively operated by the intended users (patients and caregivers) in a home, school, or community setting.
- The device is recommended and integrated into practice by clinical professionals who support individuals with feeding-related disabilities.
- The design features, controls, and user interface support efficient, effective, and satisfactory use.
- The device enables users to independently complete a minimum of five meals during a one-week trial period without undue burden on caregivers or providers.

This clinical investigation also aims to verify that supporting materials (e.g., Quick Start Guide, Instructions for Use, and MDNA form) are usable and that the overall user experience aligns with expectations for performance, ease of use, and satisfaction. These claims will be evaluated through mixed-methods data collection, including surveys and semi-structured interviews. No safety claims are being assessed in this study. Obi Gen 3 is a Class I medical device with minimal risk and has undergone benefit-risk analysis and mitigation per ISO 14971. However, participants will be monitored for device-related issues or unanticipated problems during the trial.

b) Objectives, primary and secondary, are described as ‘superiority,’ ‘non-inferiority,’ or ‘equivalence,’ if applicable.

PRIMARY: Validate whether the production equivalent enhanced Obi3 device design conforms to the formally defined user needs and intended use (per IFD-DES-054-1, Obi Validation Plan, Gen3)

SECONDARY:

- Determine patient usability in accordance with the Matching Person & Technology Assistive Technology Framework.
- Determine caregiver usability in accordance with questions from the Caregiver Burden Index.
- Determine provider perspectives following the SUS as a standardized outcome measure.
- Obtain provider feedback regarding the efficacy, efficiency, and satisfaction of the Obi clinical assessment forms and the associated process.
- Obtain other qualitative feedback regarding the perceived strengths and weaknesses of the Obi design.

c) Scientific justification and clinical relevance for effect sizes, non-inferiority margins, or equivalence limits, where applicable.

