Although this study does not include formal repeated-measures testing or time-stamped use logs, reported experience over multiple uses (i.e., across several meals and settings) will provide insight into how effectively users can learn to operate the device independently. This data will inform training recommendations and design refinements to support intuitive, low-burden use in real-world environments.

g) Pass/fail criteria to be applied to the results of the clinical investigation.

As a design validation study, the primary objective of this clinical investigation is to determine whether the Obi Gen 3 production equivalent device meets its formally documented user needs and intended use across three key stakeholder groups: patients, caregivers, and providers. The pass/fail criteria are based on usability outcomes aligned with ISO 13485 and FDA design validation requirements. The following criteria must be met for the device to be considered as having “passed” the clinical investigation:

Primary Endpoints: Acceptance criteria is based on safety and quality risk (see IFD-DES-054-1, Design Validation Plan, and IFD-DES-054-2, Design Validation Protocol). Note: Design Validation planning involves more than just human subject testing. This CIP covers only the human subject portion.

Intended Use: For all subjects that complete the 1-week trial, the following must be met:

- ICF performance qualifier for Functional Eating must drop at least one severity level (ex. “severe” to “moderate”) for 85% of patients.
- No Serious Adverse Device Effects (SADE), Serious Health Threat, or Unanticipated Serious Adverse Device Effect (USADE).

User Needs: For all subjects that complete the 1-week trial, 50% of respondents must be in favor that the requirement has been fulfilled (see IFD-DES-051-1 Validation Plan)

If the investigation meets or exceeds these thresholds across all stakeholder groups, the design will be deemed to have passed and is considered validated. If one or more criteria are not met, the results will be analyzed to determine if design modifications, additional training resources, or workflow adjustments are necessary prior to commercialization.

h) The provision for an interim analysis, criteria for the termination of the clinical investigation on statistical grounds, where applicable.

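### Section A.5 a) lists safe operation as a claim to be verified and then says no safety claim is assessed; a zero count of serious device effects would not settle it

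*Protocol*

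**What the plan says.** All references are to the protocol.

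- **A.5 a), list of claims.** The list opens with "The claims for clinical performance and effectiveness to be verified in this study include". Its first item is "The device can be safely and effectively operated by the intended users (patients and caregivers) in a home, school, or community setting". The text after the list says the claims will be evaluated with surveys and semi-structured interviews.
- **A.5 a), next sentence.** "No safety claims are being assessed in this study". It then adds that participants will be monitored for device-related issues.
- **A.1.5, synopsis.** A Primary Safety Endpoint is named: adverse events are monitored and recorded through the sponsor's existing procedure, and none are anticipated.
- **A.3 a).** The study will "confirm a favorable benefit/risk ratio".
- **A.3 c).** "This study is not intended to evaluate safety or efficacy from a regulatory or therapeutic standpoint".
- **A.7 g).** The criterion is introduced by "Intended Use: For all subjects that complete the 1-week trial, the following must be met". It allows no serious adverse device effect, no serious health threat and no unanticipated serious adverse device effect. If all thresholds are met, "the design will be deemed to have passed and is considered validated".
- **A.7 c), h) and k).** No hypothesis testing or inferential conclusion is planned. Confidence intervals may be given to describe precision.

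**The concern.** Within one subsection the protocol undertakes to verify safe operation and denies assessing any safety claim. The heading over the list speaks of performance and effectiveness, but that does not remove the conflict, because *safely* is part of the claim itself. Nor is it a single stray word: the synopsis endpoint and the benefit/risk sentence in A.3 a) also treat safety as something the study reports on.

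What is at stake is the report. The result feeds a commercialization decision, and A.17 commits to making it public. If no serious device effect occurs, an author could cite the A.5 a) list and write that safe operation was verified. A reader could cite the next sentence and reply that safety was never assessed. The document backs both. The first statement would also rest on a zero count in a small group followed for about a week, which says little about any low event rate.

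**Working it through.** **Step 1. The passages side by side.**

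| Place | What it implies about safety |
|---|---|
| A.5 a), safe-operation item | To be verified |
| A.5 a), disclaimer | Not assessed |
| A.1.5, Primary Safety Endpoint | Recorded as an endpoint |
| A.3 a) | Benefit/risk to be confirmed |
| A.3 c) | Not evaluated from a regulatory or therapeutic standpoint |
| A.7 g) | Zero serious device effects needed to pass |

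The first, third and fourth rows conflict with the second. The fifth is qualified and the sixth is a decision rule; neither needs to conflict with it.

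**Step 2. The plan's own numbers.** A.6.3 h) gives 20 patients, 20 caregivers and 20 providers: 3 × 20 = 60, as stated. A.7 e) rests this on a human factors minimum of 15 per user population. With the expected drop-out of under 10% (A.7 e), item 6), 15 / 0.90 = 16.7, rounded up to 17, so 20 is enough for that purpose. No event rate, tolerable rate or precision target for serious device effects enters the sample size, so 20 cannot be reproduced as a safety calculation.

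**Step 3. What a zero count would show.** With 0 events in *n* people, the exact one-sided 95% upper bound solves (1 − p)^n = 0.05, so p = 1 − 0.05^(1/n). The two-sided 95% limit replaces 0.05 with 0.025.

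| Denominator | n | One-sided 95% | Two-sided 95% |
|---|---|---|---|
| All patients | 20 | 1 − 0.05^(1/20) = 13.9% | 16.8% |
| Patients completing, at 10% drop-out (20 × 0.90) | 18 | 1 − 0.05^(1/18) = 15.3% | 18.5% |
| Patients plus caregivers | 40 | 1 − 0.05^(1/40) = 7.2% | 8.8% |

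The 18 applies because A.7 g) limits the criterion to subjects who complete the week. The 40 applies because the claim in A.5 a) names caregivers as well. It assumes that all 20 caregivers are exposed and that events in a patient and that patient's caregiver are independent.

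**Step 4. How often the criterion would be met.** The chance of no event is (1 − p)^n. The true rates below are assumptions, since the protocol gives none.

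| Assumed true rate | n = 20 | n = 40 |
|---|---|---|
| 1% | 82% | 67% |
| 2% | 67% | 45% |
| 5% | 36% | 13% |
| 10% | 12% | 1.5% |

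The criterion would usually expose a gross problem. It would often be met at a rate of 1% or 2%.

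**The case against.** The strongest reply is that the design is sound and only some wording is loose. Most of that stands.

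- **The zero-event criterion.** A reader might infer that a safety pass criterion is itself incompatible with making no safety claim. The document does not support this. A.7 g) works as a go/no-go rule: if a criterion is missed, the results are analysed for changes before commercialization. Nothing there says that zero events demonstrates safety. It also sits in a different section from the disclaimer.
- **A.3 c).** A reader might take it as a second flat denial. It is not. It is limited to a regulatory or therapeutic standpoint, which is compatible with watching for serious device effects during design validation.
- **Sample size.** A reader might infer that 20 patients is too few and the sample size is wrong. The protocol states no tolerable rate and disclaims inference, so there is no target for 20 to miss. The bounds limit what a zero count may be said to show; they are not an error in the calculation.
- **Other evidence.** The safety case draws on over 3,000 devices sold without an adverse event, on risk assessment and on certification (A.4), and A.7 g) notes that validation goes beyond human subject testing. That is a good reason not to ask this study to verify safety. It does not explain why A.5 a) says the study will.
- **Denominator.** Quoting only 13.9% would be one-sided, because the claim also covers caregivers. Counting them gives 7.2%, about half, and still not a rate at which safe operation could be called verified without a stated tolerance.

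What remains is the conflict between the A.5 a) claim and the disclaimer, with the synopsis endpoint and A.3 a) on the side of the claim.

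**Conclusion.** The contradiction in A.5 a) is real and should be corrected; A.1.5 and A.3 a) add to it. A pass under A.7 g) would leave two opposite statements about safety equally defensible from the text.

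Meeting the zero-event criterion would not verify safe operation. The one-sided 95% upper bound is 13.9% with 20 patients, 15.3% with 18 completers and 7.2% with 40 patients and caregivers. These figures assume full enrolment, drop-out at the 10% ceiling for the 18, independent events, and one week or so of exposure per person. Whether any of them is acceptable cannot be judged, since the protocol sets no acceptable rate.

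This is a fault in what the plan says it will conclude. It is not a fault in the criterion, the sample size or the descriptive analysis.

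**What to change.** 1. In A.5 a), remove *safely* from the opening item of the list and keep the disclaimer.
2. In A.3 a), replace the statement that the study will confirm the benefit/risk ratio with one that it contributes data to the benefit-risk file. A.4 b) already describes the results as informing an updated risk management report.
3. In A.1.5, describe the Primary Safety Endpoint as descriptive monitoring of adverse events.
4. In A.7 g), state that the serious device effect criterion is a fail trigger and not evidence of safety. Beside any zero count, report the exact upper bound and its denominator (patients enrolled, completers, or patients plus caregivers).

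The reverse repair, keeping *safely* and deleting the disclaimer, should not be used: it would make the text consistent by asserting a verification that a zero count here cannot supply.

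The cost is four wording changes and one reported bound, which A.7 c) already permits. Design, sample size and conduct are unchanged. The downside is a more modest safety statement.

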Additional Endpoints	
I.) Providers:
 
 a. System Usability Scale (SUS) retained in its standardized format b. Obi Medical Device Needs Assessment (MDNA) Form, and the overall service delivery process per SOP220. c. Optional - Semi-Structured Interview 
II.) Caregivers:
 
 a. System Usability Scale (SUS) retained in its standardized format b. Modified Matching Person and Technology (MPT) assessment. The standardization of this tool is no longer retained given the changes made, but will still provide valuable data regarding the caregivers'

	
impressions of Obi Gen 3 following the one week trial period.
 
c. Optional - Semi-Structured Interview
 
III.) Patients
 
a. Modified Matching Person and Technology (MPT) assessment. The standardization of this tool is no longer retained given the changes made, but will still provide valuable data regarding the patients' impressions of Obi Gen3 following the one week trial period.
 
b. Descriptive data regarding the patient-participants will be gathered from their completed MDNA Form.
 
c. Optional - Semi-Structured Interview

Inclusion Criteria	
 - Providers with relevant expertise to recommend and evaluate patients' ability to use Obi - Caregivers directly assisting users with Obi - Adults or children (≥ 5 years) needing assistive feeding technology to self feed
Exclusion Criteria	
 - Inability to provide informed consent/assent - Cognitive impairments that may prevent the ability to understand or respond to the survey questions - Non-English speakers (English-only materials) - Residents of California who are new Obi users

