This clinical investigation is a formative design validation study intended to assess the usability and user experience of the Obi Gen 3 Medical Robotic Feeding Device. As such, the study is not designed to test predefined effect sizes, non-inferiority margins, or equivalence limits because it does not involve comparing clinical performance outcomes between devices or interventions.

d) Primary and secondary hypotheses, if applicable.

This is not a hypothesis-driven study. This investigation aims to generate qualitative and quantitative data to determine whether the device fulfills its intended use and meets the functional and experiential needs of its users, including patients, caregivers, and providers. These data will guide product refinement, workflow integration, and stakeholder support strategies. Consequently, the scientific and clinical value lies not in statistical thresholds of performance superiority or equivalence but in identifying usability facilitators and barriers. Validated assessment tools used in the study (e.g., Matching Person & Technology Framework, System Usability Scale) provide benchmarks and interpretation guidelines (e.g., SUS score of ≥ 68 as average usability), which will be used for contextualizing findings. These interpretive thresholds will help determine whether observed results meet clinically meaningful usability standards and support progression to broader deployment. While formal hypotheses regarding effect size or non-inferiority do not apply to the design and objectives of this study, the clinical relevance is embedded in stakeholder feedback, validated usability scores, and evidence that the device enables functional independence as intended.

e) Risks and anticipated adverse device effects that are to be assessed.

The Obi Gen 3 Medical Robotic Feeding Device is classified as a Class I medical device under FDA and MDR regulations, indicating minimal risk to users. As such, no significant adverse device effects are anticipated in the context of this usability study.

See section A4 for identified risks.

A.6. Design of Clinical Investigation

A.6.1. General

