This clinical investigation is a non-randomized, non-comparative usability study designed to evaluate whether the Obi Gen 3 Medical Robotic Feeding Device conforms to its intended use and meets documented user needs. The purpose of the study is not to assess therapeutic effectiveness or to compare outcomes across intervention groups but to validate device usability and stakeholder satisfaction across real-world settings.

Given the nature and objectives of the study, randomization, blinding, and allocation concealment are not applicable. However, several measures will be taken to minimize or avoid bias and manage potential confounding factors:

1. Standardized Protocols and Training

All participants (providers, caregivers, and patients) will engage with the device under a standardized study protocol, including consistent onboarding materials, instructional documents, and usage expectations (e.g., a minimum of five meals during the trial period). These materials were developed based on prior formative feedback and are provided in uniform formats to reduce variability in participant experience.

2. Structured Data Collection Tools

Usability feedback will be collected using validated instruments (e.g., System Usability Scale, Matching Person & Technology framework) and semi-structured interview guides. These tools ensure consistency in gathering information, reduce interviewer bias and facilitate comparisons across stakeholder groups.

3. Triangulation of Stakeholder Perspectives

The study design allows for triangulation of findings by including data from three distinct stakeholder groups (providers, caregivers, and patients). This multi-perspective approach reduces the risk of single-source bias and provides a broader understanding of device usability in real-world contexts.

4. Post-Use Feedback After Trial Exposure

Participants provide their usability ratings and feedback only after completing the one-week trial. This approach helps minimize expectation bias and ensures responses reflect the user experience with the device.

5. Blinding of Data Analysts (if applicable)

The Principal Investigator will conduct the data analysis but will not be involved directly in participant recruitment or data collection, reducing the potential for confirmation bias during the interpretation of results.

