- Standardized Training and Materials**

All participants—including providers, caregivers, and patients—will receive consistent onboarding materials (e.g., Quick Start Guide, Instructions for Use) to ensure a common understanding of device setup and use. This minimizes variability in use procedures across stakeholder groups and supports equitable engagement with the device.

- Use of Validated Frameworks**

The study utilizes established and validated tools, including the System Usability Scale (SUS), Matching Person & Technology (MPT) Framework to assess usability across diverse participants. These tools allow for meaningful interpretation of findings and reduce subjective bias.

- **Mitigation of Risks**

Identified study risks—such as user fatigue, frustration, and data privacy concerns—are managed through:

- Brief participation windows (e.g., 1-week trial with a minimum of 5 meal uses),
- Technical support availability,
- Secure data collection via the HIPAA-compliant Qualtrics platform,
- Clear data management protocols for de-identification and limited access

- **Minimization of Confounding Variables**

Participants are pre-screened using a standardized process (SOP220) to ensure that only individuals meeting inclusion criteria are enrolled. Demographic and baseline data, including functional feeding status and assistive technology experience, are collected to allow subgroup analyses and account for potential confounders in interpretation.

- **Triangulation of Data (Mixed Methods)**

A mixed-methods design integrates both quantitative data (e.g., rating scales) and qualitative data (e.g., semi-structured interviews), allowing for comprehensive understanding and internal validation of usability findings across stakeholder perspectives.

- **Consistent Scheduling and Follow-Up**

Data collection occurs at fixed time points following the trial period (e.g., immediately post-trial and optional 1-month follow-up), which supports consistent comparison across users. All interviews are conducted using a semi-structured guide to reduce interviewer variability.

- **Independent Oversight and Conflict of Interest Management**

To preserve data integrity and transparency, a conflict of interest management plan is in place for the Principal Investigator. This includes institutional oversight and disclosure of funding and sponsor relationships in study materials and reporting.

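### The modified Matching Person and Technology (MPT) scale is called validated and credited with benchmarks although the synopsis says it is no longer standardized, so no benchmark claim on the secondary patient-usability endpoint is supported

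*Protocol*

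**What the plan says.** Three sections give the MPT the standing of a validated instrument:

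- A.5 d): "Validated assessment tools used in the study (e.g., Matching Person & Technology Framework, System Usability Scale) provide benchmarks and interpretation guidelines". The one numeric example that follows is "SUS score of ≥ 68 as average usability". The next sentence gives the benchmarks a purpose: "These interpretive thresholds will help determine whether observed results meet clinically meaningful usability standards and support progression to broader deployment".
- A.6.1 b), among the measures against bias: "Usability feedback will be collected using validated instruments", with the SUS and the MPT as the examples.
- A.6.4 d), in the item on validated frameworks: "The study utilizes established and validated tools, including the System Usability Scale (SUS), Matching Person & Technology (MPT) Framework".

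The synopsis (A.1.5, Additional Endpoints) describes the MPT differently. For caregivers and again for patients, it labels the MPT as modified and adds: "The standardization of this tool is no longer retained given the changes made". What it expects from the tool in patients is modest: it "will still provide valuable data regarding the patients' impressions of Obi Gen3". The SUS has another status, "System Usability Scale (SUS) retained in its standardized format", and is listed for providers and caregivers but not for patients. Sections A.6.1 c) and A.6.1 e) also call the MPT adapted.

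In the analysis text, A.6.1 d) applies established scoring thresholds to the SUS only. A.7 b) has the rating scales, the MPT among them, summarised by descriptive statistics.

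**The concern.** Benchmarks and interpretation rules belong to an instrument in the form in which they were established. They cannot be assumed to carry over once the content is changed, and the protocol cites no work on the modified form. A.5 d) speaks of the tools used in this study, so it cannot be read as describing only the published original. It therefore credits the modified MPT with a property that the synopsis says was given up.

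This matters because A.5 d) gives the benchmarks a role: they help to settle whether results reach a clinically meaningful usability standard and support deployment. An author of the final report who follows A.5 d) could write that patient usability met the benchmark of a validated scale. Nothing in the protocol would support that sentence.

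**Working it through.** No arithmetic decides this point, and the plan has no figure of its own to reproduce. The check is a comparison of what the protocol says about each instrument, who completes it, and which thresholds are given.

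**Step 1. Status of the two rating scales.**

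| Instrument | A.5 d), A.6.1 b), A.6.4 d) | Synopsis A.1.5 | A.6.1 c) and e) |
|---|---|---|---|
| SUS | validated | standardized format kept | used as named |
| MPT | validated | modified, standardization not kept | adapted |

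The SUS is described consistently. The MPT is not.

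**Step 2. Who completes which scale** (A.1.5 Additional Endpoints; A.6.1 c); group sizes from A.6.3 h)).

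| Group | Target n | SUS | Modified MPT |
|---|---|---|---|
| Providers | 20 | yes | no |
| Caregivers | 20 | yes | yes |
| Patients (5 adults, 15 children) | 20 | no | yes |

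The other patient questionnaire is the study's own survey. The synopsis (Study Design) describes the surveys as non-standardized. Patients therefore complete no usability scale in standardized form. They are 20 of 20 + 20 + 20 = 60 participants, one third of the study.

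**Step 3. Benchmarks actually stated.** For the SUS there is one, a score of 68 or more. For the MPT there is none: no cut-off and no reference score appears anywhere in the protocol. The SUS value cannot serve the patients, who have no SUS score.

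**Step 4. Where the gap has an effect.** Patient usability is the first secondary endpoint in A.6.1 c), and the adapted MPT is its only named measure. The gap falls there. The criteria in A.7 g) are:

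- improvement by at least one level on the ICF qualifier for functional eating in 85% of patients;
- no serious device effects or serious health threats;
- 50% of respondents in favor that a user need is fulfilled.

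None of these uses the MPT, so none changes with its status.

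**The case against.** The strongest reply is that the operative text already treats the MPT correctly. The synopsis discloses the loss of standardization and reduces the tool to a source of impressions. A.6.1 d) applies thresholds to the SUS only, A.7 b) makes the MPT descriptive, and the only numeric benchmark is the SUS one. On this view the conflict is a loose adjective in three narrative sections of a study that tests no hypothesis. Most of this stands, and it limits the consequence. It does not remove the contradiction: A.5 d) names the MPT among the tools that provide benchmarks and then gives those benchmarks a role in the deployment judgement. A statistical analysis plan could add scoring detail, but it would not correct the protocol's conflicting statements about the instrument.

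A reader might infer more than the documents support:

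- **That patients have no decision criterion at all.** A.7 g) gives them two thresholds that do not depend on the MPT: the ICF qualifier and the user-needs responses.
- **That the problem covers caregivers too, 40 of 60 participants.** Caregivers also complete the modified MPT, but they keep the standardized SUS and its benchmark.
- **That the modified MPT has been shown to be invalid.** The synopsis says that standardization is lost and does not mention validity. The extent of the changes cannot be seen from the protocol.
- **That a comparison with published MPT scores is planned.** No section schedules one. The risk is that A.5 d) would appear to permit it.
- **That the bias control fails.** A.6.1 b) credits the tools with consistent data collection and less interviewer bias. A uniform electronic questionnaire can give that without norms. What goes too far is the word *validated* for the MPT and, in A.6.4 d), the credit that the tools lessen subjective bias because they are validated.

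**Conclusion.** The contradiction is real. Three sections describe the MPT used in the study as validated, and A.5 d) says that it supplies benchmarks with a part in judging usability. The synopsis says that this version is modified and no longer standardized. No MPT benchmark is stated, and the one stated benchmark belongs to a scale that patients do not complete.

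The size is limited to one secondary endpoint, patient usability, in 20 of 60 participants. For that endpoint no standardized usability scale supports a benchmark claim. No sample size, planned calculation or pass/fail criterion in A.7 g) is affected.

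This rests on two assumptions. First, the synopsis describes the MPT version that will actually be given. Second, A.7 g) states the acceptance criteria in full for this purpose; it refers to separate design validation documents that are not at hand. The point should be corrected because the fix is almost free and the text as it stands invites a conclusion on patient usability that the data could not carry.

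**What to change.** In A.5 d), A.6.1 b) and A.6.4 d), restrict *validated* and *benchmarks* to the SUS. In the same sections, state that the modified MPT is a non-standardized measure, that it is summarised descriptively, that it is not compared with published MPT scores, and that it has no role in deciding whether usability standards are met. This brings the three sections into line with the synopsis, A.6.1 d) and A.7 b). Whether the descriptive summary is by item, subscale or total can be left to the statistical analysis plan; nothing in the protocol requires one of these.

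The cost is a wording change to the protocol, with no new data and no change to the instruments. The price in interpretation is that conclusions on patient usability become more modest: they can report patients' impressions after the trial week, but not that a validated standard was reached.
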